7.4.2 Electroretinogram (ERG)

Full-field ERG responses include 30 Hz flicker; photopic single flash a- and b-waves; scotopic cone-rod flash a- and b-waves; and scotopic rod, dim white light b-wave. Amplitudes and implicit times will be presented in tabular format and graphically by patient and cohort for study eye and fellow eye as appropriate. Mean changes from baseline will also be summarized. Clinically significant changes, defined as a decrease in ERG amplitude of greater than 50%, from Day -28 ERG data will be indicated and listed where appropriate.

Peak amplitudes (nV/deg²) and latency (ms) values for multifocal ERG (mfERG) responses at Day -28 will be tabulated for each of six concentric rings in the visual field by patient and eye. The concentric ring minimum and maximum are collected separately. The minimum and maximum are summed together to obtain the peak amplitude (nV/deg²). To examine change

in mfERG responses in the central visual field across visits, the mean changes from Day -28 across the peak amplitudes and latencies of inner rings (Rings 1-3) will be tabulated and plotted against time by cohort, patient and eye. In addition, mean changes across the peak amplitude and latencies of outer rings (Rings 4-6) will also be tabulated and plotted by cohort, patient and eye against time.

7.4.3 Visual Function Questionnaire (VFQ-25)

All VFQ-25 responses will be re-coded to a scale of 0 to 100 following the scoring rules provided by the questionnaire. The mean of all re-coded scores will determine the score for each patient, which will range from 0 to 100. The scores for the 12 VFQ-25 sub-scales will also be provided, if appropriate. Change in the VFQ-25 responses from Day -1 to Week 48 will be tabulated by patient and cohort and 95% confidence limits and/or ranges will be provided. Meaningful changes from Day -1 will be highlighted where appropriate.

7.4.4 Supplementary Reading Center Data

Fundus photography photomontage, fundus autofluorescence (FAF), and microperimetry data will all be analyzed separately by Translational Clinical Trials Center (TCTC) at Casey Eye Institute, the Central Reading Center at the end of the study. These exploratory measures will not be summarized for DSMB meetings.

7.5 Other Endpoints

7.5.1 Immunology

The number and percentage of patients with antibody responses to any UshStat component at all relevant time points will be tabulated by dose cohort.

7.5.2 Biodistribution Endpoint

The number and percentage of patients with UshStat detected in the blood and urine by PCR at all relevant time points will be tabulated by cohort (See Section 2 of protocol for specific visits). These data may not be available for review between cohorts but will be reported when available.

7.6 Safety Analysis

The primary, secondary and additional outcomes described in the preceding sections pertain mostly to assessing patient safety. The only additional safety assessment will be the determination of the MTD.

7.6.1 Determination of Maximum Tolerated Dose (MTD)

The MTD will be defined as the highest dose level that has an acceptable safety and tolerability and positive benefit/risk profile in the opinion of the DSMB.

8.0 A LIST OF PROPOSED TABLES/FIGURES

This section contains a list of proposed tables and figures that will be presented in analysis of study data, but not all figures and tables will be included in DSMB reports. At a minimum, figures and tables from [Sections 8.1](#) through [8.4.2](#) will be included in DSMB reports, but additional figures and tables from remaining sections will be included when possible.

8.1 Patient Flow and Compliance

Table 1A will summarize patient compliance with the follow-up schedule. Visits occurring past the protocol required date will be indicated where appropriate. Those that have not yet been completed, but remain within the allowed window (See Section 2 of the study protocol) will be highlighted in green.

Table 1A: Screening and Surgery Dates and Visit Completion by Cohort

Patient ID	Cohort	Study Eye	Screen1 Date	Screen2 Date	Surgery Date	Day1 Date	Week1 Date	Week2 Date	Week4 Date	Week12 Date	Week24 Date	Week36 Date	Week48 Date
------------	--------	-----------	--------------	--------------	--------------	-----------	------------	------------	------------	-------------	-------------	-------------	-------------

Figure 1B graphically displays screened patients, patients deemed ineligible at Pre-dose Visit 1 and Pre-dose Visit 2, as well as the reasons for ineligibility. It also reflects eligible patients and those being treated at Day 0.

[figure not shown]

Table 1C will list the overall numbers and percentages of patients completing and withdrawing from the study, and these values will also be stratified by cohort. Reasons for withdrawal, including death will be provided where applicable.

Table 1C: Study Follow-up Completion and Withdrawal (including deaths)

Cohort	Completed	Withdrawals
	N (%)	N (%)
1		
2		
3		
4		
5		
Total		

8.2 Baseline Characteristics

Table 2A will summarize Baseline demographic information for all patients and stratify the information by cohort.

Table 2A: Demographics Summary by Cohort

		Enrolled Patients (N=X)	Cohort 1 (N=X)	Cohort 2 (N=X)	Cohort 3 (N=X)	Cohort 4 (N=X)	Cohort 5 (N=X)
AGE (years)	Median (Range)	X (X-X)	X (X-X)	X (X-X)	X (X-X)	X (X-X)	X (X-X)
GENDER	Female	N (%)	N (%)	N (%)	N (%)	N (%)	N (%)
	Male	N (%)	N (%)	N (%)	N (%)	N (%)	N (%)
RACE	American Indian or Alaskan Native	N (%)	N (%)	N (%)	N (%)	N (%)	N (%)
	Asian	N (%)	N (%)	N (%)	N (%)	N (%)	N (%)
	Black or African American	N (%)	N (%)	N (%)	N (%)	N (%)	N (%)
	Native Hawaiian or other Pacific Islander	N (%)	N (%)	N (%)	N (%)	N (%)	N (%)
	Other	N (%)	N (%)	N (%)	N (%)	N (%)	N (%)
	White	N (%)	N (%)	N (%)	N (%)	N (%)	N (%)
	Hispanic or Latino	N (%)	N (%)	N (%)	N (%)	N (%)	N (%)
ETHNICITY	Not Hispanic or Latino	N (%)	N (%)	N (%)	N (%)	N (%)	N (%)
	HEIGHT (cm)	Median (Range)	X (X-X)				
WEIGHT (kg)	Median (Range)	X (X-X)	X (X-X)	X (X-X)	X (X-X)	X (X-X)	X (X-X)

Table 2B will list demographic information by patient.

Table 2B: Detailed Demographic Listing by Cohort

Patient Cohort	Patient ID			Age	Gender	Race	Ethnicity	Height (cm)	Weight (kg)

Table 2C will give a summary of individual patient medical history. Further detailed table(s) may be provided where appropriate.

Table 2C: General Medical History by Patient

Patient ID	Exam Date	Cardio-vascular	Hematology/ Oncology	Psych- iatric	Gastro- intestinal	Neurologic	Endocrine	Nephrologic	Resp- iratory	Autoimmune	Musculo- skeletal	Allergies	Non-Ocular Surgery

Table 2D will summarize Baseline physical examination parameters for all patients by cohort. Individual patient profiles will also include physical examination information, laboratory values, vital signs, etc. at Baseline as well as during follow-up. See Section 9 for patient profile examples.

Table 2D: Baseline Physical Examination Parameters by Cohort

		All Eligible Patients	Cohort 1	Cohort 2	Cohort 3	Cohort 4	Cohort 5
Cardiovascular Assessments	Normal	N (%)	N (%)	N (%)	N (%)	N (%)	N (%)
	Abnormal	N (%)	N (%)	N (%)	N (%)	N (%)	N (%)
Dermatologic Assessments	Normal	N (%)	N (%)	N (%)	N (%)	N (%)	N (%)
	Abnormal	N (%)	N (%)	N (%)	N (%)	N (%)	N (%)
Endocrine/Metabolic Assessments	Normal	N (%)	N (%)	N (%)	N (%)	N (%)	N (%)
	Abnormal	N (%)	N (%)	N (%)	N (%)	N (%)	N (%)
GI Assessments	Normal	N (%)	N (%)	N (%)	N (%)	N (%)	N (%)
	Abnormal	N (%)	N (%)	N (%)	N (%)	N (%)	N (%)
Genitourinary Assessments	Normal	N (%)	N (%)	N (%)	N (%)	N (%)	N (%)
	Abnormal	N (%)	N (%)	N (%)	N (%)	N (%)	N (%)
Head/ENT Assessments	Normal	N (%)	N (%)	N (%)	N (%)	N (%)	N (%)
	Abnormal	N (%)	N (%)	N (%)	N (%)	N (%)	N (%)
Lymphatic/Hematologic Assessments	Normal	N (%)	N (%)	N (%)	N (%)	N (%)	N (%)
	Abnormal	N (%)	N (%)	N (%)	N (%)	N (%)	N (%)
Musculoskeletal Assessments	Normal	N (%)	N (%)	N (%)	N (%)	N (%)	N (%)
	Abnormal	N (%)	N (%)	N (%)	N (%)	N (%)	N (%)
Neurologic Assessments	Normal	N (%)	N (%)	N (%)	N (%)	N (%)	N (%)
	Abnormal	N (%)	N (%)	N (%)	N (%)	N (%)	N (%)

		All Eligible Patients	Cohort 1	Cohort 2	Cohort 3	Cohort 4	Cohort 5
Psychologic Assessments	Normal	N (%)	N (%)	N (%)	N (%)	N (%)	N (%)
	Abnormal	N (%)	N (%)	N (%)	N (%)	N (%)	N (%)
Respiratory Assessments	Normal	N (%)	N (%)	N (%)	N (%)	N (%)	N (%)
	Abnormal	N (%)	N (%)	N (%)	N (%)	N (%)	N (%)

Table 2E will give a summary of individual patient reproductive status.

Table 2E: Reproductive Status by Patient

Patient ID	Hysterectomy	Vasectomy	Tubal ligation	Postmenopausal	Other

Patient profiles will provide notable ocular history at baseline for each patient in tabular format. Please refer to Section 9 for examples of patient profiles.

8.3 Primary Outcome Analyses

8.3.1 Adverse Events

Table 3A lists the total and percentage of patients (overall and by cohort) experiencing no TEAE, any severe or serious TEAEs, a TEAE resulting in death and any TEAE related to IMP or the procedure. **Tables 3B to 3I** will include the MedDRA version used for grading as a footnote. All of the AEs presented will be graded using the same MedDRA version. **Tables 3B and 3C** summarize TEAEs and patients with at least one TEAE by MedDRA SOC, HLT, PT, severity and cohort and **Table 3D** summarizes treatment emergent AESIs by MedDRA SOC, HLT, PT, severity and cohort.

Table 3A: Number and Percentage of TEAEs and Patients Experiencing TEAEs or No Events by Type of Event and Cohort

Type of Event	Patients						Events					
	All	Cohort 1	Cohort 2	Cohort 3	Cohort 4	Cohort 5	All	Cohort 1	Cohort 2	Cohort 3	Cohort 4	Cohort 5
Fatal	N (%)	N (%)	N (%)	N (%)	N (%)	N (%)	N (%)					
No Events	N (%)	N (%)	N (%)	N (%)	N (%)	N (%)	N (%)					
Related to IMP	N (%)	N (%)	N (%)	N (%)	N (%)	N (%)	N (%)					
Related to Procedure	N (%)	N (%)	N (%)	N (%)	N (%)	N (%)	N (%)					
Serious	N (%)	N (%)	N (%)	N (%)	N (%)	N (%)	N (%)					
Severe	N (%)	N (%)	N (%)	N (%)	N (%)	N (%)	N (%)					

Table 3B: Number of TEAEs by MedDRA SOC, HLT, PT, Severity and Cohort (Event-based Counts)

SYSTEM ORGAN CLASS	HIGH LEVEL TERM (HLT)	PREFERRED TERM (PT)	COHORT								All Cohorts	
			1		2		3		4			
			Mild	Mild	Moderate	Mild	Moderate	Severe	Mild	Moderate	Mild	
SOC1	HLT1	PT1										
		PT2										
SOC2	HLT1											
		PT1										
		PT2										
All												

**Table 3C: Number of Patients Experiencing TEAEs by MedDRA SOC, HLT, PT, Severity and Cohort
(Patient-based Counts)**

(Note that if more than one event in each category is reported for a single patient, the most recent event of maximum severity is counted.)

SYSTEM ORGAN CLASS (SOC)	HIGH LEVEL TERM (HLT)	PREFERRED TERM (PT)	COHORT								All Cohorts	
			1		2		3		4			
			Mild	Mild	Moderate	Mild	Moderate	Severe	Mild	Moderate	Mild	
SOC1	HLT1	PT1										
		PT2										
SOC2	HLT1											
		PT1										
		PT2										
All												

**Table 3D: Number of TEAEs of Special Interest by MedDRA SOC, HLT, PT, Severity and Cohort
(Event-based Counts)**

SYSTEM ORGAN CLASS (SOC)	HIGH LEVEL TERM (HLT)	PREFERRED TERM (PT)	COHORT									
			1		2		3		4		All Cohorts	
			Mild	Mild	Moderate	Mild	Moderate	Severe	Mild	Moderate	Mild	Moderate
SOC1	HLT1	PT1										
		PT2										
	HLT1											
		PT1										
		PT2										
All\												

Tables 3E and 3F summarize TEAEs and patients with at least one TEAE by MedDRA SOC, HLT, PT, severity and cohort, with all inflammatory events grouped into a single PT.

**Table 3E: Number of TEAEs by MedDRA SOC, HLT, PT, Severity and Cohort with Inflammatory Events Grouped
(Event-based Counts)**

SYSTEM ORGAN CLASS (SOC)	HIGH LEVEL TERM (HLT)	PREFERRED TERM (PT)	COHORT									
			1		2		3		4		All Cohorts	
			Mild	Mild	Moderate	Mild	Moderate	Severe	Mild	Moderate	Mild	Moderate
SOC1	HLT1	PT1										
		PT2										

		COHORT										All Cohorts			
		1	2	3				4		All Cohorts					
		Mild	Mild	Moderate	Mild	Moderate	Severe		Mild	Moderate	Mild	Moderate	Severe		
SOC2	HLT1														
	PT1														
	PT2														
All															

Table 3F: Number of Patients Experiencing TEAEs by MedDRA SOC, HLT, PT, Severity and Cohort with Inflammatory Events Grouped (Patient-based Counts)

(Note that if more than one event in each category is reported for a single patient, the most recent event of maximum severity is counted.)

			COHORT										All Cohorts			
			1	2	3				4		All Cohorts					
			Mild	Mild	Moderate	Mild	Moderate	Severe		Mild	Moderate	Mild	Moderate	Severe		
SYSTEM ORGAN CLASS (SOC)	HIGH LEVEL TERM (HLT)	PREFERRED TERM (PT)														
SOC1	HLT1	PT1														
		PT2														
SOC2	HLT1															
	PT1															
	PT2															
All																

Tables 3G and 3H summarize patients with at least one TEAE related to IMP and procedure, respectively, by MedDRA SOC, HLT, PT, severity and cohort.

Table 3G: Number of TEAEs Related to IMP by MedDRA SOC, HLT, PT, Severity and Cohort (Patient-based Counts)

SYSTEM ORGAN CLASS	HIGH LEVEL TERM (HLT)	PREFERRED TERM (PT)	COHORT								All Cohorts	
			1		2		3		4			
			Mild	Mild	Mild	Moderate	Mild	Moderate	Severe	Mild	Moderate	Severe
SOC1	HLT1	PT1										
		PT2										
SOC2	HLT1											
		PT1										
		PT2										
All												

Table 3H: Number of TEAEs Related to Procedure by MedDRA SOC, HLT, PT, Severity and Cohort (Patient-based Counts)

SYSTEM ORGAN CLASS	HIGH LEVEL TERM (HLT)	PREFERRED TERM (PT)	COHORT								All Cohorts	
			1		2		3		4			
			Mild	Mild	Mild	Moderate	Mild	Moderate	Severe	Mild	Moderate	Severe
SOC1	HLT1	PT1										
		PT2										

COHORT												
SOC2	HLT1	1		2		3		4		All Cohorts		
		Mild	Mild	Moderate	Mild	Moderate	Severe	Mild	Moderate	Mild	Moderate	Severe
SOC2	HLT1											
	PT1											
	PT2											
	All											

[Tables 3I](#) and [3J](#) list AEs prior to treatment and TEAEs by patient and cohort, respectively. [Table 3K](#) lists all adverse events of special interest (AESI).

Table 3I: Listing of Adverse Events Prior to Treatment by Patient and Cohort

Cohort	Patient ID	Enroll Date	AE Description	Event Date	Severity of Event	Outcome	Duration (Days)	MedDRA Classification		
								System Organ Class	High Level Term	Preferred Term
<hr/>										

Table 3J: Listing of TEAEs by Patient and Cohort

Cohort	Patient ID	Surgery Date	AE Description	Event Date	Outcome	Duration (Days)	Severity of Event	Relatedness		MedDRA Classification		
								Relation to Investigational Medicinal Product	Relation to Surgery	System Organ Class	High Level Term	Preferred Term
<hr/>												

Cohort	Patient ID	Surgery Date	AE Description	Event Date	Outcome	Duration (Days)	Severity of Event	Relatedness		MedDRA Classification		
								Relation to Investigational Medicinal Product	Relation to Surgery	System Organ Class	High Level Term	Preferred Term

Table 3K: Listing of Treatment Emergent Adverse Events of Special Interest by Patient and Cohort

Cohort	Patient ID	Surgery Date	AE Description	Event Date	Outcome	Duration (Days)	Severity of Event	Relatedness		MedDRA Classification		
								Relation to Investigational Medicinal Product	Relation to Surgery	System Organ Class	High Level Term	Preferred Term

8.3.2 BCVA, Ocular Inflammation and IOP

Table 3L lists the primary outcomes of BCVA, ocular inflammation and IOP for the study and fellow eyes by patient and visit, Tables 3M and 3N summarize mean changes in BCVA and IOP, respectively, by cohort and visit for the study and fellow eyes and Table 3O summarizes the number and percentage of individuals with elevated (≥ 25 , ≥ 30 and ≥ 35 mmHg) IOP in the study eye. Changes in ophthalmic inflammation by dose group, visit and eye will also be summarized in Table 3P. Ophthalmic outcome data will be displayed graphically in plots similar to Figures 3Q and 3R. Tables and plots will be given for the study eye as well as for the fellow eye, and labeled appropriately.

Table 3L: Ophthalmic Outcome Listing for Study Eye and Fellow Eye by Patient and Visit

Patient ID	Visit	Study	IOP		BCVA		Anterior Cells		Anterior Flare		Vitreous Cells		Vitreous Haze		Macular Edema	
			Fellow	Study	Study	Fellow	Study	Fellow	Study	Fellow	Study	Fellow	Study	Fellow	Study	Fellow

Table 3M: Mean Changes from Pre-surgical BCVA by Cohort and Visit

Cohort	Visit	Study Eye					Fellow Eye				
		N	Mean	Std	Min	Max	N	Mean	Std	Min	Max

Table 3N: Mean Changes from Pre-surgical IOP by Cohort and Visit

[figure not shown]
Cohort	Visit	Study Eye					Fellow Eye				
		N	Mean	Std	Min	Max	N	Mean	Std	Min	Max

Table 3O: Patients Experiencing Elevated IOP in the Study Eye Following Treatment by Cohort

Cohort	IOP ≥ 25 mmHg				IOP ≥ 30 mmHg				IOP ≥ 35 mmHg			
	No		Yes		No		Yes		No		Yes	
	N	%	N	%	N	%	N	%	N	%	N	%
1												
2												
3												
4												
5												
All												

[figure not shown]
Table 3P: Changes in Ophthalmic Inflammation in the Study Eye by Cohort and Visit

Cohort	Visit	Anterior Chamber Cells		Anterior Chamber Flare		Vitreous Cells				Vitreous Haze			
		No Change	Half-Step Increase	No Change	1-Step Increase	Half-Step Decrease	No Change	Half-Step Increase	2-Step Decrease	1-Step Decrease	No Change	Half-Step Increase	
		N	%	N	%	N	%	N	%	N	%	N	%

Figure 3Q: Ophthalmic Outcomes Over Time (Days from Surgery) by Patient

Mean changes from Baseline (Day -28) will be plotted for ophthalmic outcomes versus dose cohort in a plot similar to Figure 3R.

Figure 3R: Mean Change in Ophthalmic Outcome from Baseline by Dose Cohort

8.3.3 Laboratory Parameters

Laboratory parameters will be listed for each patient in the patient profiles indicating lab values above or below the clinical site's normal ranges. Table 3S lists the patients that had abnormal and/or clinically significant lab values.

Table 3S: Listing of Patients with Abnormal and/or Clinically Significant Labs¹

Site	Patient ID	Age	Gender	Weight (kg)	Visit	Category	Lab	Value	Normal Limits
------	------------	-----	--------	-------------	-------	----------	-----	-------	---------------

¹Lab values that are in bold are clinically significant.

Table 3T summarizes mean changes from Baseline for each continuous laboratory parameter.

Table 3T: Mean Change in Continuous Laboratory Parameters by Cohort and Visit

Lab Category	Lab Name	Cohort	Visit	N	Quartiles			95% CI		
					Mean	Std	25%	50%	75%	Lower

8.3.4 OCT

Table 3U lists OCT data by patient. This information will also be included in patient profiles. See Section 9 for patient profile examples. Figures similar to 3Q and 3R may also be used to summarize continuous OCT endpoint variables.

Table 3U: OCT Listing by Patient and Visit

Patient ID	Visit	Central Macular Thickness		Macular Volume		Increase in Cystoid Macular Edema		Unfavorable Change in Subretinal Fluid		Comments	
		Study	Fellow	Study	Fellow	Study	Fellow	Study	Fellow	OCT Data	Study

8.3.5 Vital Signs

Table 3V summarizes median vital signs by cohort and visit. A listing of vital signs by visit will be provided in each patient's profile report (see Section 9). Clinically significant changes or abnormalities will be noted.

Table 3V: Vital Signs

Cohort	Visit	Temperature Median (Min, Max)		Blood Pressure Median (Min, Max)			Pulse Median (Min, Max)
		Degrees Fahrenheit	Degrees Celsius	Respiration Median (Min, Max)	Systolic	Diastolic	

8.4 Secondary Outcome Analyses

8.4.1 Full-field Kinetic and Static Perimetry

Individual and mean static perimetry data will be presented similarly to other ophthalmic outcome data as in Figures 3L and 3M. Individual scotoma as measured by kinetic perimetry may be represented graphically where appropriate in a patient profile. Tables 4A and 4B list static (GATE) and kinetic (SKP) data, respectively, by cohort, patient and visit for both study and fellow eyes.

Table 4A: Static (GATE) Perimetry Data by Patient

Cohort	Patient ID	Visit	Volume of Full Field (Decibel Steradians)		Hill of Vision Fellow	111pt grid- Volume of Full Field Hill of Vision (Decibel Steradians)	
			Study			Study	Fellow

Table 4B: Kinetic (SKP) Perimetry Data by Patient

[figure not shown]
Cohort	Patient ID	Visit	I4E Isopter Area (Squared Degrees)		III4E Isopter Area (Squared Degrees)		V4E Isopter Area (Squared Degrees)		VI4E Isopter Area (Squared Degrees)	
			Study	Fellow	Study	Fellow	Study	Fellow	Study	Fellow

8.4.2 ERG

Table 4C lists full field ERG response amplitudes (microvolts) and implicit times (ms) parameters by patient and visit for the study eye. Fellow eye data will be summarized similarly. The a- and b- wave amplitudes and implicit times may be represented graphically, similar to Figure 4D by patient and cohort as appropriate. Mean change in full field ERG will also be summarized. Clinically significant changes from Day -28 in ERG data will be indicated and listed where appropriate.

Table 4C: Full Field ERG Response (Study Eye) Amplitude and Implicit Time Data by Cohort, Patient and Visit

Cohort	Patient ID	Visit	30 Hz Flicker		Photopic Single Flash (a-wave)		Photopic Single Flash (b-wave)		Scotopic Cone-Rod (a-wave)		Scotopic Cone-Rod (b-wave)		Scotopic Rod (dim, b-wave)	
			Amplitude	Implicit Time	Amplitude	Implicit Time	Amplitude	Implicit Time	Amplitude	Implicit Time	Amplitude	Implicit Time	Amplitude	Implicit Time

Figure 4D: Full Field ERG Data Over Time

Tables 4E, 4F and 4G list the mean peak amplitude and latencies for each patient at Day -28 for each ring, mean changes in these values for the central (Rings 1-3) visual field and mean changes for the peripheral (Rings 4-6) visual field, respectively. Figures 4H and 4I illustrate the change in peak and latency values for the central and peripheral visual fields, respectively, against time for each patient.

Table 4E: Mean Peak Amplitudes and Latencies at Baseline (mfERG) by Cohort and Patient

Cohort	Patient ID	Study Eye	Ring 1		Ring 2		Ring 3		Ring 4		Ring 5		Ring 6	
			OD	OS										

Table 4F: Central Field (Rings 1-3) Summary mfERG Data by Cohort and Patient

Cohort	Patient ID	Study Eye	Mean Central Field (Baseline)		Mean Change (Week 24)		Mean Change (Week 48)	
			OD	OS	OD	OS	OD	OS

Table 4G: Peripheral Field (Rings 4-6) Summary mfERG Data by Cohort and Patient

Cohort	Patient ID	Study Eye	Mean Peripheral Field (Baseline)		Mean Change (Week 24)		Mean Change (Week 48)	
			OD	OS	OD	OS	OD	OS

[figure not shown]
[figure not shown]
Figure 4H: Change in Central Field (Rings 1-3) mfERG Response Over Time

Figure 4I: Change in Peripheral Field (Rings 4-6) mfERG Response Over Time

8.4.3 VFQ-25

At the end of the study, mean change in VFQ-25 scores will be tabulated by cohort (Table 4J) and may be summarized using plots similar to those in Figures 3L and 3M. Please refer to Section 8.3.2 for these plots.

Table 4J: Change in VFQ-25 by Cohort

Cohort	Mean (SD) Change VFQ-25	95% Confidence Limits

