5.2 Secondary Endpoints

The secondary objective is to evaluate UshStat for possible biological activity. An attempt will be made to determine a delay in retinal degeneration following subretinal injection of UshStat, through changes in function relative to the untreated contralateral eye using the following retinal analytical techniques:

- BCVA
- Indirect ophthalmoscopy
- Visual function questionnaire (VFQ-25)
- Full dilated slit-lamp examination
- Fundus photography – photomontage
- Visual field testing: Semi-automated Kinetic Perimetry (SKP), Full-Field GATE Static Perimetry, and microperimetry
- Autofluorescence

- Electroretinogram (ERG)
- OCT

The primary time points for secondary endpoints will be considered the Week 24 (6-month) and Week 48 (12-month) visits.

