The purpose of this memorandum is to document that the Table of Contents for the final analysis for TDU13600 will differ from the Table of Contents in the currently approved version 2 of the SAP, dated 22JUL2016. The format of the tables will be the same as those in the SAP, except that the adverse event tables will be updated to the format used for the 23MAY2018 DSMB Report for SAR422459. The TOC and the adverse event table shells to be used for the final TLFs are included below.

Coordinating Center

Statistician Signature:

[figure not shown]
Date: 30AUG2019

Sponsor Statistician

Signature:

[figure not shown]
Date: 04SEP2019

Coordinating Center

Director Signature:

Date: 24SEP2019

TOC FOR ALL TLFs FOR TDU13600

- [Table 1A](#): Screening and Surgery Dates and Visit Completion by Cohort
- [Figure 1B](#): Patient Flow Diagram
- [Table 1C](#): Study Follow-up Completion and Withdrawal (including deaths)
- [Table 2A](#): Demographics Summary by Cohort
- [Listing 2B](#): Detailed Demographic Listing by Cohort
- [Listing 2C](#): General Medical History by Patient
- Listing 2D: Study Eye Ocular History by Patient
- Listing 2E: Fellow Eye Ocular History by Patient
- [Table 2F](#): Baseline Physical Examination Parameters by Cohort
- Table 2G: Reproductive Status by Patient
- Listing 2H: Detailed Surgery Listing by Patient
- Table 3A: Number and Percentage of Patients Experiencing TEAEs or No Events by Type of Event and Cohort
- Table 3B: Number of Patients Experiencing TEAEs by MedDRA SOC, HLGT, HLT, PT, and Cohort
- Table 3C: Number of Patients with TEAEs of Special Interest by MedDRA SOC, HLGT, HLT, PT, and Cohort
- Table 3D: Number of Patients with SAEs by MedDRA SOC, HLGT, HLT, PT, and Cohort
- Table 3E: Number of Patients Experiencing Inflammatory TEAEs by MedDRA SOC, HLGT, HLT, PT, and Cohort
- Table 3F: Number of Patients with TEAEs Related to IMP by MedDRA SOC, HLGT, HLT, PT, and Cohort
- Table 3G: Number of Patients with TEAEs Related to Procedure by MedDRA SOC, HLGT, HLT, PT, and Cohort
- [Table 3H](#): Listing of Adverse Events Prior to Treatment by Patient and Cohort
- [Table 3I](#): Listing of TEAEs by Patient and Cohort
- [Table 3J](#): Listing of Treatment Emergent Adverse Events of Special Interest by Patient and Cohort
- Table 3K: Listing of Treatment Emergent Serious Adverse Events by Patient and Cohort
- [Listing 3L](#): Ophthalmic Outcome Listing for Study Eye and Fellow Eye by Patient and Visit

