- [Table 3M](#): Mean Changes from Pre-surgical BCVA by Cohort and Visit
- [Table 3N](#): Mean Changes from Pre-surgical IOP by Cohort and Visit

- Table 3O: Patients Experiencing BCVA Change in the Study Eye at Week 48 Following Treatment by Cohort
- Table 3P: Patients Experiencing Elevated IOP in the Study Eye at Week 48 Following Treatment by Cohort
- **Tables 3Q-3S:** Changes in Ophthalmic Inflammation in the Study Eye by Cohort and Visit
- Figures 3T-3V: BCVA in Study and Fellow Eyes by Patient in Cohort X
- Figures 3W-3Y: IOP in Study and Fellow Eyes by Patient in Cohort X
- Figure 3Z: Mean Changes in BCVA in the Study Eye over Time by Cohort
- Figure 3AA: Mean Changes in IOP in the Study Eye over Time by Cohort
- **Listing 3BB:** Listing of Patients with Abnormal and/or Clinically Significant Labs
- Listing CC: Abnormal Physical Examination Listing by Patient
- **Table 3DD:** Mean Change in Continuous Laboratory Parameters by Cohort and Visit
- **Listing 3EE:** OCT Listing by Patient and Visit
- Figures 3FF-3HH: Central Retinal Thickness (OCT) for Study and Fellow Eyes in Cohort X
- Figures 3II-3KK: Macular Volume (OCT) for Study and Fellow Eyes in Cohort X
- Table 3LL: Change from Baseline in Vital Signs by Cohort and Visit
- **Listing 4A:** Static (GATE) Perimetry Data by Patient
- Figures 4B-4D: Volume of Full Field Hill of Vision Measured by Static (GATE) Perimetry by Patient in Cohort X
- Figures 4E-4G: 111pt grid-Volume of Full Field Hill of Vision Measured by Static (GATE) Perimetry by Patient in Cohort X
- **Listing 4H:** Kinetic (SKP) Perimetry Data by Patient
- Figures 4I-4K: SKP Data in Study Eyes by Patient in Cohort X
- **Listing 4L:** Full Field ERG Response (Study Eye) Amplitude and Implicit Time Data by Cohort, Patient and Visit
- **Table 4M:** Mean Peak Amplitudes and Latencies at Baseline (mfERG) by Cohort and Patient
- **Table 4N:** Central Field (Rings 1-3) Summary mfERG Data by Cohort and Patient
- **Table 4O:** Peripheral Field (Rings 4-6) Summary mfERG Data by Cohort and Patient
- Listing 5A: Detailed Listing of Immunologic Results from Blood Samples by Cohort and Patient
- Listing 5B: Biodistribution Endpoint Data

ADVERSE EVENT TABLE SHELL FOR TDU13600

PRIMARY SYSTEM ORGAN CLASS HLGT: High Level Group Term HLT: High Level Term Preferred Term n(%)	Cohort 1 (1.4×10^5 TU) (N=3)	Cohort 2 (4.7×10^5 TU) (N=3)	Cohort 3 (1.4×10^6 TU) (N=3)	All Cohorts (N=9)
Any Class	X (X%)	X (X%)	X (X%)	X (X%)
SOC1	X (X%)	X (X%)	X (X%)	X (X%)

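### The 2019 final output list has no VFQ-25 output for a planned secondary endpoint, and leaves unclear whether fellow-eye full-field ERG will be produced

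*SAP*

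**What the plan says.** VFQ-25 is scheduled at the baseline visit and Week 48 (Protocol Section 2). SAP Section 7.4.3 sets the analysis: "Change in the VFQ-25 responses from Day -1 to Week 48 will be tabulated by patient and cohort", with 95% confidence limits and/or ranges. SAP Section 8.4.3 assigns the end-of-study output: "mean change in VFQ-25 scores will be tabulated by cohort" (Table 4J).

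SAP Section 5.2 frames the secondary endpoints as assessed "through changes in function relative to the untreated contralateral eye using the following retinal analytical techniques". For full-field ERG, SAP Section 7.4.2 has amplitudes and implicit times "presented in tabular format and graphically by patient and cohort for study eye and fellow eye as appropriate". SAP Section 8.4.2 gives Table 4C for the study eye and adds: "Fellow eye data will be summarized similarly".

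SAP Section 7.0 commits to presenting every result that contributes to the primary and secondary endpoints, and to reporting ophthalmic results for both eyes where available.

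The memorandum dated 30 August 2019 says that the final table of contents will differ from that of SAP version 2. Its list is headed "TOC FOR ALL TLFs FOR TDU13600". It contains no VFQ-25 entry. Its one full-field ERG entry, Listing 4L, reads "Full Field ERG Response (Study Eye) Amplitude and Implicit Time Data by Cohort, Patient and Visit".

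**The concern.** A list that presents itself as complete is what the programmers will build from. If a secondary endpoint is not on it and no other route is stated, the endpoint will not be reported, although it was defined, scheduled and given a table. VFQ-25 is also the only patient-reported measure among the SAP's secondary endpoints, so nothing else on the list stands in for it.

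The full-field ERG question matters because the untreated eye is the study's control (Protocol Section 4.10). Full-field ERG change shown for the study eye alone cannot be set against natural progression. If the list is read literally, that comparison is missing for this component of the ERG endpoint.

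**Working it through.** No power or error-rate figure bears on this point. The check is a comparison of the two output lists.

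**1. Secondary outputs in SAP Section 8.4 against the 2019 list**

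| SAP version 2 | Content | 2019 list |
|---|---|---|
| Table 4A | Static perimetry, both eyes | Listing 4A |
| Table 4B | Kinetic perimetry, both eyes | Listing 4H |
| Table 4C | Full-field ERG, study eye | Listing 4L |
| Figure 4D | Full-field ERG over time | none |
| Table 4E | Multifocal ERG at baseline | Table 4M |
| Table 4F | Multifocal ERG, central rings | Table 4N |
| Table 4G | Multifocal ERG, peripheral rings | Table 4O |
| Figure 4H | Multifocal ERG change, central | none |
| Figure 4I | Multifocal ERG change, peripheral | none |
| Table 4J | VFQ-25 change by cohort | none |

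Of 10 outputs, 6 are carried over and 10 − 6 = 4 are not. Three of those four are figures, and their measures are still listed or tabulated in Listing 4L and Tables 4N and 4O. Table 4J is the only one whose measure disappears altogether.

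**2. Is VFQ-25 reported by another route?**

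- SAP Section 5.2 names nine measures. Three have no entry in the 2019 list: VFQ-25, fundus photomontage and autofluorescence.
- SAP Section 7.4.4 sends photomontage and autofluorescence, with microperimetry, to separate analysis by the reading center. That leaves 3 − 2 = 1 measure without a stated route: VFQ-25.
- The patient-profile shells in SAP Section 9, as far as they are readable, have no VFQ-25 panel.
- The minimum DSMB package in SAP Section 8.0 ends at Section 8.4.2, just before VFQ-25 in Section 8.4.3.

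**3. Full-field ERG in the fellow eye**

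- Separately titled fellow-eye outputs: 0 in SAP version 2 and 0 in the 2019 list.
- SAP version 2 covered that eye by a sentence in Section 8.4.2. The memo does not withdraw the sentence, and it keeps the SAP table formats except for adverse events.
- Elsewhere the 2019 list names the fellow eye where it is meant: Listings 2E and 3L, Figures 3T–3Y and Figures 3FF–3KK.
- The SAP shells behind the multifocal ERG Tables 4M–4O have columns for right and left eye, so that part of the ERG endpoint keeps its comparator.
- The mean-change summary of full-field ERG promised in SAP Sections 7.4.2 and 8.4.2 is not listed either.

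**4. How much the missing table would show**

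The final shells have 3 patients in each of 3 cohorts, 9 in all. For n = 3 the 95% t-interval is mean ± t(0.975; 2 df) × SD/√3 = mean ± (4.303/1.732) × SD = mean ± 2.48 SD. Cohort means will be very imprecise, so the by-patient values in SAP Section 7.4.3 carry most of the information.

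**The case against.** The strongest reply is that the memo is an open, dated document with sponsor and coordinating-center sign-off dates. It says that its contents differ from the SAP, and SAP Section 1.0 leaves deviations to be described in the final study report, which is not among the documents reviewed. A reader might infer concealment; the memo's own statement rules that out. What is missing is an itemized list of removals and a reason. A deviation note in the report would explain the gap but would not supply the result.

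A reader might also infer selective reporting after VFQ-25 results had been seen. The documents do not support this. They give no database-lock date, VFQ-25 was to be tabulated only at the end of the study, and it lies outside the minimum DSMB package. Open-label treatment does not show that anyone had summarized the scores.

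On ERG, a reader might infer that the 2019 memo removed the control eye. The study-eye title is the same as that of SAP Table 4C, so it cannot show a change made in 2019, and multifocal ERG keeps both eyes. What stands is an ambiguity about the full-field component.

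Finally, absence from the list does not by itself mean that a measure goes unreported, as Section 7.4.4 shows. That objection does not reach VFQ-25, which Section 7.4.4 does not cover. It is also fair that VFQ-25 is scored per patient and cannot give a study-versus-fellow-eye contrast, that the study is descriptive, and that no dose or safety decision in the documents rests on Table 4J. These limit the consequence but do not remove the commitment in SAP Section 7.0.

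**Conclusion.** The VFQ-25 part is established. One planned secondary endpoint, with a defined analysis and a planned table, has no output in a list headed as complete, no stated alternative route and no reason for its absence. All 9 patients in the final shells are affected. The fellow-eye full-field ERG part is narrower: the list does not say whether the output promised in SAP Section 8.4.2 will be made, and it should.

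The conclusion assumes that the list is exhaustive, as its heading says, and that no VFQ-25 panel sits in unreadable parts of the patient-profile shells. It makes no claim about motive or about who had seen what. The consequence is incomplete reporting of biological activity. The safety evaluation is not affected. The point is worth correcting because the correction is small.

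**What to change.** 1. Add SAP Table 4J to the memo's list: VFQ-25 change from Day -1 to Week 48 by cohort, with the by-patient values that SAP Section 7.4.3 calls for (the Table 4J shell itself is by cohort only). It needs a new number, because the memo now uses 4I–4K for kinetic perimetry figures; 4P is the next free label.
2. Extend Listing 4L to both eyes, or add a fellow-eye listing in the Table 4C layout.
3. In the same revision, itemize the other SAP Section 8.4 outputs not carried over (Figures 4D, 4H and 4I, and the full-field ERG mean-change summary), with a short reason for each.

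The cost is one table from an existing shell, a by-patient listing, one fellow-eye listing in an existing layout, and a short memo revision. The plan already schedules collection of the data, and the design does not change.
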